14.4 SAMPLE SIZE AND ACCRUAL

14.4.1 MERLIN COHORT OF ACUTE AND RECENT HIV INFECTION

Our goal is to enroll the total of participants who enrolled in the SABES step 3 study.

14.4.2 MERLIN SUB-STUDIES

40 participants will be separately consented and enrolled in sub-studies of qualitative integration of HIV reservoirs (leukapheresis) and neuro-inflammation; and 60 participants will also be separately consented for studies of GI microbiome (rectal biopsy/secretion). These participants may choose to participate in one, two, or all of the elective evaluations which require a separate consent and specific procedures as outlined in this protocol and corresponding SSPs.

14.5 MONITORING

All endpoints will be calculated and monitored on a quarterly basis throughout the period of enrollment and treatment.

14.6 ANALYSES

14.6.1 TESTING OF URINE, AND DRIED BLOOD SPOTS

Since high-level alcohol use is an exposure of interest, detailed questionnaire data will be collected and biologic specimens will be analyzed at least once a year to monitor use of alcohol and other substances (cocaine, marijuana).

14.6.2 MEASUREMENT OF THE HIV RESERVOIR

It is likely that early ART prevents the establishment of the long-lived latent reservoir, and this hypothesis is supported by several lines of evidence. However, to date almost all studies investigating this question have used PCR-based assays, which overestimate the size of the reservoir [12] because they do not distinguish between cells with defective, replication-incompetent cells vs. productively infected cells and the small pool of long-lived, latently infected cells. Conversely, the viral outgrowth assays measure only resting CD4+ T cells with replication competent HIV and likely underestimate the size of the reservoir [55]. Therefore, it is still unclear when and where the latent replication-competent reservoir is seeded. Our collaborator, [name], has recently developed a novel assay (Tat/Rev Induced Limiting Dilution Assay, "TILDA") that can more precisely measure the frequency of productively and latently infected cells in a clinical sample as various times after infection. This assay measures the frequency of cells harboring inducible HIV without the above-mentioned limitations of standard assays (Figure 2). By combining ultrasensitive detection of multiply spliced (ms) RNAs upon T cell receptor stimulation together with a limiting dilution assay, this method allows [name] lab to measure a frequency of cells harboring transcriptionally silent - nonetheless inducible – viruses. To our knowledge, this viral induction assay is the only method that allows the measurement of the frequency of cells harboring inducible virus that can be performed with less than a million CD4+ T cells.

[figure not shown]

Figure 2: HIV RNA induction assay. Sorted CD4+ T cells are stimulated for 12 hours with PMA/ionomycin. Serial dilutions of the stimulated cells are distributed in a 96-well plate and digested. Multi-spliced HIV RNA are detected in a 2-step real time PCR. The maximum likelihood method is used to calculate the frequency of cells with inducible HIV RNA based on the number of positive well.

14.6.3 INNATE IMMUNE RESPONSES AND INFLAMMATION

Innate immune cells are the major drivers of the inflammation that is required to mount protective immune responses and mount a rapid response after HIV acquisition [14]. The innate immune cells involved in this response are diverse in their phenotypes and functions. Cytokines secreted by these cells influence the maturation and development of effector cells that drive humoral and cellular immune responses to HIV. Molecular interactions of these cells with cells of the adaptive immune system also impact quantitative and qualitative features of primary and recall immune responses. It is likely that the balance among immune modulating factors induced shortly after HIV acquisition determines the strength and character of the adaptive immune response to infection as well as the size and characteristics of the HIV reservoir.

Using multiparameter flow cytometry we will: 1) enumerate T cells, B cells, monocytes, myeloid dendritic cells, plasmacytoid dendritic cells; and 2) perform in depth immunophenotyping of T cells, including markers of maturation (e.g., CD45RO/CD27), differentiation (e.g., into TH1, TH2, TH17, and/or Treg subsets), activation (e.g., Ki67, CD38, HLA-DR, and/or PD-1), and cytokine production (e.g., of IL-2, -4, -7, -16, TNF, and IFNy). In addition, using plasma samples, we will measure markers of chronic inflammation (e.g., CRP, D-dimer, sCD14, and an array of chemokines and cytokines) using commercially available ELISA kits and multiplex assays, as well as activity of the immunomodulatory kynurenine pathway of tryptophan catabolism [kynurenine:tryptophan ratio] using LC-MS/MS as described previously. In addition, our collaborators, Drs. [name] and [name], will use transcriptional profiling to measure changes in innate immune responses, cell activation markers and inflammatory mediators associated with HIV acquisition and in response to HIV infection and ART treatment. RNA-Seq transcriptomic profiling in his laboratory will provide an unbiased and sensitive tool to evaluate immune responses. This comprehensive approach will include the quantitative and qualitative assessment of the multiple pro- and anti-inflammatory pathways and their regulation; these parameters are not generated when performing conventional assays to measure cytokines.

14.6.4 DYSBIOSIS OF THE GUT MICROBIOTA AND CORRELATION WITH MARKERS OF HIV-ASSOCIATED IMMUNOPATHOLOGY.

Early HIV-associated damage to gastrointestinal mucosa and subsequent translocation of microbial products into the systemic circulation are thought to play a central role in the inflammatory changes associated with AIDS and non-AIDS related morbidities. Recent studies have shown that untreated HIV-infected subjects exhibit dysbiosis - a markedly different composition of the gut bacterial microbiota [19, 56]. This dysbiosis persists in some during ART, and the extent of dysbiosis correlates with activity of the kynurenine pathway of tryptophan catabolism and plasma concentrations of the inflammatory cytokine interleukin-6 (IL-6), two established markers of disease progression.

Stool specimens taken during untreated acute/recent infection, and after ART initiation will be processed and submitted to 16S rRNA-based phylogenetic characterization of microbiome composition in the laboratory of our collaborator, [name]. DNA will be extracted from stool and rectal biopsy/secretion samples using a protocol optimized for the isolation of bacterial DNA [57]. Exploratory data analyses will seek to identify operational taxonomic units (OTUs) that change in abundance as a result of acute HIV infection and to determine whether the abundance of such OTUs is linked to markers of immune activation and viral reservoir seeding. Furthermore, comparisons of the composition of distinct microbial community samples will be utilized to understand if initiation of early ART is associated with a gut microbiota that more resembles the

pre-infection state as compared to microbiota from subjects who initiate ART later after HIV acquisition. Multiple specimens from the same participant will be analyzed to assess how the timing of initiation of ART affects the long-term make-up of the GI microbiome. Urine will also be used to examine microbiome function through measurement of urinary metabolites.

14.6.5 DNA INTEGRATION SITES

Drs. [name] and [name] will characterize and compare the HIV DNA integration sites in subjects with and without high-level alcohol use who started ART in Fiebig stages I-II, III-V and in the deferred ART arm. Among participants with sustained suppression of HIV RNA to undetectable levels, a total of 45 participants (~15 subjects from each group) will be studied upon enrollment (prior to the initiation of ART), and after 3.5 years of ART. PBMC from the subset of participants agreeing to leukapheresis will be preferentially selected for these studies.

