Design: The MERLIN Study extends the follow-up of participants enrolled in the SABES Study, a study of ~250 MSM and TW in Lima with acute and recent HIV infection enrolled in an early vs. deferred antiretroviral treatment study. The MERLIN study will offer follow-up to all of the patients enrolled in the SABES study, prioritizing the participants who also were enrolled in a related Observational Study, in which baseline peripheral blood mononuclear cell (PBMC) isolation sampling was conducted. Additionally to the participants previously enrolled in SABES, up to 25 additional participants with acute HIV diagnosis will be enrolled directly in this study and will be treated immediately upon diagnosis.

Consenting eighteen-year old or older MSM and TW, who participated and received ART in the SABES Study and who have acceptable hematologic, liver, and renal function will be considered to participate in the MERLIN study, in which they will continue a 3-drug ART regimen.

Because of the low number of participants, which acute infection who received immediate treatment in the SABES study and who could be eligible for MERLIN, a new enrollment and follow-up cohort will be open with up to 25 participants (see above). In this cohort, participants with acute HIV infection will initiate antiretroviral treatment immediately after receiving diagnosis and will also be followed up for an extended time.

Duration: Up to 5 years from enrollment on this protocol (through 2022) with visits timed referencing date of HIV diagnosis and original SABES study visits (or SABES enrollment if applicable).

Treatment Regimen:

In *SABES* Step 3, participants had been randomized to either one of the following arms: Immediate Arm: to immediately receive ART for 48 weeks; or Deferred Arm: to delay treatment for 24 weeks (unless Peruvian criteria for initiation of treatment are met), and then receive ART at 24 weeks.

For the purposes of correlative studies, participants in the Immediate Arm are further categorized as initiating Immediate ART (in Acute HIV: Fiebig I/II) or Early ART (Recent HIV: Fiebig III/V) infection.

The MERLIN participants will initiate the co-formulation EVG/COBI/FTC/TDF (Genvoya) for its component TAF.

EVG/COBI/FTC/TDF is not readily available in private or public sector HIV care in Peru, but it is considered acceptable based on FDA-approval and US-based HIV guidelines to the Peruvian Ministry of Health (MOH).

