4.2.6 HIV Integration Sites

Recent studies of individuals who initiated ART during chronic infection [34, 35] indicate that HIV integration into genes associated with cancer or cell cycle regulation confers a survival advantage to specific cells, apparently the result of increased proliferation and formation of clonal populations that persist during suppressive ART. Identifying which early integration events lead to proliferation and persistence of infected cells may suggest novel interventions to reduce or clear the HIV reservoir that is limited in size due to early ART. We expect that participants who initiate ART early vs. later after primary infection will have fewer unique integration sites prior to initiation of ART and at 18 and 42 months will have fewer proviruses in genes associated with cancer and cell proliferation. Also, we expect that AUD will correlate with T cell activation and inflammatory markers. Therefore, we hypothesize that individuals with low alcohol use will have relatively fewer unique integration sites at all time-points compared to those with high use who initiate ART at the same Fiebig stage, and at 18 and 42 months will have fewer proviruses in genes associated with cancer and cell proliferation.

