6.1 PRIMARY OBJECTIVES

- 1) To determine the relative long-term benefits of immediate vs. early vs. deferred initiation of ART.

Initiation of ART during Fiebig I-II, while theoretically appealing, is currently infeasible in clinical practice because the duration of FI-II is very short (10 days) and because antibody-based tests, used almost world-wide, are unable to diagnose FI-II. Six months of ART initiated shortly after seroconversion (FIII) can improve many immune parameters, although not to the near normal level seen when ART is initiated during FI-II [3]. Longer-term follow-up of seropositive participants who started ART ~2-8 months after HIV acquisition compared to those initiating ART during FI-II is needed to see whether markers of inflammation and residual viral load might continue to improve after 6 months, decreasing the difference between the groups. Methods: We will evaluate the 3 groups using specimens from equivalent times after ART initiation through the first 5 years of ART usage, comparing CD4 counts, time to undetectable VL, GI microbiota, and inflammatory markers. The size of the replication-competent HIV reservoir in PBMCs will be compared using measurements of multiply spliced viral RNA (msRNA) and the degree of low-level infection of new cells by assessing the production of circular viral DNA (2LTR HIV DNA). We will model the size and persistence of the viral reservoir across all ART-adherent study participants. In a subset of individuals from each group, the proviral integration sites will

be defined at ART initiation and after 1.5 and 3.5 years to assess the maintenance of the reservoir by proliferating CD4 cells. We will continue evaluating endpoints annually or biannually, as long as participants remain on study.

- 2) To determine the impact of high-level alcohol use on the relative long-term benefits of immediate vs. early vs. delayed ART initiation

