Dysbiosis is present in individuals with high-level alcohol use [23, 24, 27, 45-47] and in many HIV-infected patients. The extent of dysbiosis correlates with established markers of HIV disease progression and the consequent inflammatory processes contribute to HIV disease progression, even in treated individuals. *Methods*: We will use monthly self-report data on alcohol use as well as alcohol biomarkers in blood and hair to assess alcohol consumption as a continuous, time-varying predictor. In all participants at the time of diagnosis, and at multiple time points prior to ART in those enrolled into the deferred group, we will assess VL, GI microbiota, pro-inflammatory cytokines, and HIV reservoirs. We will compare these factors between subjects by their reported alcohol use, focusing on events occurring shortly after HIV acquisition. Specimens from uninfected and chronically infected subjects are available as controls. Finally, among ART-adherent subjects with persistent viral suppression, we will HIV DNA integration sites in those with and without high-level alcohol use at 1.5 and 3.5 years after ART initiation.

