7.1 GENERAL STUDY DESIGN

This protocol for the MERLIN study describes the extended follow-up of participants enrolled in the *SABES* study, a study of ~250 HIV+ MSM and TGW in Lima, Perú. In this study, we will enroll up to 25 individuals with acute HIV infection.

The *SABES* study: The ongoing *SABES* study combines laboratory and epidemiologic data with

modeling to investigate the hypothesis that early ART initiation and management of alcohol use disorder will prevent onward HIV transmission among MSM/TGW diagnosed with acute (FI-FII: Ab-/HIV RNA+) or recent (≤ 3 months) HIV infection (FIII-V). The SABES study population is MSM and transgender women (TGW) not using feminizing hormones (all referred to as "MSM" from here on) in Lima. This study is being conducted in 3 phases: 1) HIV screening, 2) monthly follow-up testing of HIV-uninfected participants by point-of-care EIA and NAAT testing for HIV RNA in pools of seronegative specimens (pools are run daily), and 3) enrollment of MSM with incident HIV infection into a randomized ART treatment study (Figure 1). Only participants with acute (seronegative but HIV RNA+) or recent HIV infection (EIA+ with a prior HIV-negative test within 3 months) are eligible for enrollment in the treatment phase of the SABES study. These participants are stratified by acute vs. recent infection and randomized 1:1 to Immediate arm (to receive ART immediately) or Deferred arm (to receive ART beginning at 24 weeks or when the participant meets Peruvian treatment initiation thresholds, whichever comes first) (Figure 1). We completed enrollment of 225 HIV+ participants into the SABES study by the end of March 2016. A small number (5-10) of additional participants will be enrolled in SABES; those with symptomatic acute HIV infection will receive ART immediately, in accordance with current Peruvian treatment guidelines and will therefore not be randomized to possibly delay ART. The Human Subjects section contains a discussion of risks and benefits. All SABES participants received either EFV/FTC/TDF or EVG/COBI/FTC/TDF as first line medication. Virologic suppression at 48 and 96 weeks is equivalent for both regimens when used as initial treatment [48]; however because EVG/COBI/FTC/TDF may result in more rapid viral suppression we began using EVG/COBI/FTC/TDF for new participants when it became available as a donated drug in late 2015.

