10.3.4.10 Leukapheresis

A subset of MERLIN participants (N = 40) will undergo leukapheresis. There is a separate consent form and only those who are newly enrolled and volunteer for this procedure will have it performed. Qualitative and quantitative assessment of the HIV reservoir (including its localization in different CD4⁺ T cell subsets) will require large numbers of cells, which is important as both size and distribution of the HIV reservoir will be key factors in strategies to induce a functional cure. Thus, we will use leukapheresis to collect large samples at critical time points (SABES baseline and 24 weeks on all participants, then 72, 120, and 216 weeks for deferred arm, and 96, 144, and 196 weeks for immediate Arm).

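### Section 14.6.5 measures integration sites at enrolment and 3.5 years, while the primary objectives call for ART initiation, 1.5 and 3.5 years; in the Deferred arm the enrolment sample precedes the delay under study

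*Protocol*

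**What the plan says.** Section 14.6.5 compares integration sites in about 15 participants from each of three groups (ART started in Fiebig I-II, in Fiebig III-V, or deferred), with and without high-level alcohol use. These participants "will be studied upon enrollment (prior to the initiation of ART), and after 3.5 years of ART".

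Section 6.1, primary objective 1, says that the sites will "be defined at ART initiation and after 1.5 and 3.5 years to assess the maintenance of the reservoir by proliferating CD4 cells". Primary objective 2 compares participants "with and without high-level alcohol use at 1.5 and 3.5 years after ART initiation".

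Section 4.2.6 gives the hypotheses. Earlier starters "will have fewer unique integration sites prior to initiation of ART and at 18 and 42 months" are expected to carry fewer proviruses in cancer and proliferation genes; that is how the sentence continues. For ART timing, then, the count of unique sites is a claim about the time before ART, and the 18- and 42-month claim concerns where the proviruses sit. For alcohol, fewer unique sites are expected at every time point.

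In SABES (Section 7.1), participants were "stratified by acute vs. recent infection and randomized 1:1 to Immediate arm (to receive ART immediately) or Deferred arm", the latter "to receive ART beginning at 24 weeks or when the participant meets Peruvian treatment initiation thresholds, whichever comes first". The Executive Summary (Treatment Regimen) adds that "participants in the Immediate Arm are further categorized as initiating Immediate ART (in Acute HIV: Fiebig I/II) or Early ART" according to stage.

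**The concern.** The analysis section does not collect what the objectives and hypotheses need, and it departs from them in two unrelated ways.

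The first is the anchor of the pre-ART sample. The hypothesis is that a longer wait for ART leaves more unique integration sites by the time ART begins. To see that, the Deferred arm must be sampled after the wait. A sample at enrolment is pre-ART, but it is also pre-delay.

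The second is the missing 1.5-year measurement. Without it the early on-ART comparison in both primary objectives, and the 18-month hypothesis, would go untested if Section 14.6.5 were followed as written.

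**Working it through.** **1. The plan's own count.** 3 groups × about 15 = 45, as stated. Two time points give 45 × 2 = 90 assays. Three give 45 × 3 = 135. The difference is 45.

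**2. Sampling times side by side.**

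| Source (Protocol) | Pre-ART sample | 1.5 years of ART | 3.5 years of ART |
|---|---|---|---|
| 4.2.6, hypotheses | before ART | yes (18 months) | yes (42 months) |
| 6.1, objective 1 | at ART initiation | yes | yes |
| 6.1, objective 2 | none named for integration sites | yes | yes |
| 14.6.5, analysis | at enrolment | no | yes |

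Amendment Letters 1 to 3 do not revise Section 14.6.5. Letter 3 adds another version: it places the evaluation of the main objectives at years 2 and 4 of ART.

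**3. Which enrolment is meant.** Under Section 8.1.1, SABES participants enter MERLIN already on ART. A pre-ART enrolment sample from them can therefore only come from SABES enrolment. For newly enrolled acute cases (Group D), MERLIN enrolment is itself pre-ART, with treatment within 72 hours (Section 10.3.2.2).

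**4. Untreated time captured by the pre-ART sample.** Let T be the weeks from SABES enrolment to actual ART start: about 0 in the Immediate and Early groups, and up to 24 in the Deferred arm.

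- Sample at ART initiation (6.1): post-enrolment untreated time = T, so Deferred exceeds the others by up to 24 weeks.
- Sample at enrolment (14.6.5): post-enrolment untreated time = 0 in every group, so the delay contributes nothing.

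**5. What a difference at enrolment would mean.** The Immediate group is all acute and the Early group all recent. The Deferred group is a mixture. If stratified randomisation gives Deferred the same acute share as the treated arm, the approximate group sizes in Section 4.1 imply:

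- in-depth set (20 and 35): 20 / 55 = 36%, or 5.5 of 15;
- whole cohort (35 and 72): 35 / 107 = 33%, or 4.9 of 15.

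The three groups can therefore differ at enrolment through stage alone. Restriction to sustained suppression, and preference for leukapheresis participants, can add selection differences. None of this is an effect of ART delay.

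**6. Can the 1.5-year sample be had?** 1.5 × 365.25 / 7 = 78.3 weeks of ART.

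- Immediate and Early: study week 78.3. The week 72 visit, ±8 weeks, spans 64 to 80, which contains it.
- Deferred starting at week 24: 24 + 78.3 = 102.3. The week 96 visit spans 88 to 104, which contains it.

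The Section 10.1 table schedules PBMC at both visits. Letter 3 stops PBMC collection only after week 192 (Immediate) or 216 (Deferred).

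**7. If change from the pre-ART sample were analysed.** From enrolment to 3.5 years of ART, the Deferred interval would consist of T untreated weeks plus 3.5 years on ART; in the other groups it would be almost entirely on ART. Growth in sites before treatment would then be mixed with persistence on treatment, in one group only.

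**The case against.** The strongest defence is that Section 14.6.5 does ask for a sample before ART, in nearly the terms of Section 4.2.6, and that only Section 6.1 says ART initiation. It also describes a comparison by alcohol use, for which an enrolment sample is useful. Integration sites concern a subset of about 45 and are not named in the endpoint lists of Section 14.3. These points stand. They limit the weight of the matter, but they do not make an enrolment sample informative about a delay that has not yet happened.

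Several stronger readings are tempting and are not supported:

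- *That randomisation makes the compared groups equal at enrolment, so the planned test is null by design.* A zero expected difference holds only between the randomised Immediate and Deferred arms, within the acute and recent strata, before selection into this subset. Section 14.6.5 compares three groups, two of which are defined by stage.
- *That the Deferred change from baseline runs 24 weeks longer.* The section names no change analysis, and 24 weeks is a maximum, because ART could start earlier under the national thresholds.
- *That the 18-month hypothesis has no data.* Specimens are scheduled and Section 6.1 commits to the assay; only Section 14.6.5 omits it.
- *That leukapheresis secures the needed samples.* Section 10.3.4.10 lists "SABES baseline and 24 weeks on all participants", but Amendment Letter 2 replaced that schedule with one containing neither time.
- *That the missing 1.5-year sample causes the Deferred problem.* The two faults are independent.

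**Conclusion.** Section 14.6.5 contradicts Section 6.1 on the timing of the integration-site measurements, and the contradiction has consequences. In the Deferred arm the pre-ART sample is placed up to 24 weeks before ART, ahead of the exposure whose effect Section 4.2.6 sets out to detect. Separately, one of the two on-ART measurements promised in both primary objectives is missing from the analysis.

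This rests on reading enrolment as SABES enrolment for former SABES participants, which their being on ART at MERLIN entry compels. It assumes no effect size, variance or power; the Protocol gives none for this analysis. The bias in a change analysis is conditional on such an analysis being done. The contradiction should be resolved before the assays are run. It affects a subset analysis serving both primary objectives, not the trial as a whole.

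**What to change.** In Section 14.6.5:

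1. Take the pre-ART measurement from the last stored specimen before each participant's actual ART start. In the Deferred arm this is about week 24, or earlier where ART began earlier; a fixed week 24 would be an on-ART sample for early starters.
2. Label any SABES-enrolment sample as baseline, and state which enrolment is meant for former SABES participants and for Group D.
3. Add the 1.5-year measurement from PBMC at about week 72 (Immediate and Early) or week 96 (Deferred), choosing the visit by actual time on ART.
4. If the 1.5-year assays will not be run, delete the 18-month and 1.5-year integration-site statements from Sections 4.2.6 and 6.1.
5. Reconcile these times with the years 2 and 4 wording in Amendment Letter 3.

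The cost is protocol wording plus up to 45 further assays for the 1.5-year point. Keeping a separate enrolment baseline in the Deferred group as well would add about 15.

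Specimens are the practical limit. Section 4.1 describes large PBMC collections throughout follow-up for participants from the latter half of SABES, and Section 7.1 lists a week 24 specimen visit, but extensive sampling began only at participant 110. Anyone who entered MERLIN after the week 72 or 96 visit may also lack a 1.5-year specimen, since visits resume at the next scheduled week (Section 10.3.2.1). The number of participants with usable specimens at each time should be counted before the text is finalised.
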